FDA has cleared rTMS for major depressive disorder. rTMS is a noninvasive method to cause depolarization or hyperpolarization of neurons in the brain. It uses electromagnetic induction to induce weak electric currents using a rapidly changing magnetic field; this can cause activity in specific or general parts of the brain with minimal discomfort, allowing the functioning and interconnections of the brain to be studied. Most rTMS treatment protocols are carried out with unified stimulation parameters, such as dorsolateral left prefrontal cortex (DLPFC) stimulation for patients with major depressive disorder using a10 Hz repetitive pulse at 120% of motor threshold (MT), 5 days a week for 6 weeks. (See **Table 1** below) A variety of TMS protocols have been tested as a treatment tool for various neurological and psychiatric disorders including migraine, stroke, Parkinson's disease, dystonia, tinnitus, depression, and auditory hallucination. Mayer et al. concludes that some participants may derive long-term benefit from the rTMS course. (Mayer, Aviram, Walter, Levkovitz, & Bloch, 2012) However, there is a lack of clinical trials to show the safety and efficacy of rTMS in persons with PTSD.

The rTMS system to be used in this study has been shown to have an excellent safety profile, with nearly all adverse events being minor. In a review (Janicak, et al., 2008) of three rTMS studies involving 325 patients, no serious adverse event was reported that was due to the rTMS treatment. During acute treatment, the most common adverse event was headache, reported in 58.2% of active and 55.1% of sham groups. Headache was assessed by the study investigator as "severe" in 4.2% of active TMS and 5.1% of sham groups. Transient headache, which resolves spontaneously or with mild analgesics, is the most common adverse effect of rTMS in adults. Site pain was reported by 35.8% in active TMS group and 3.8% in the sham group. Pain was reported as "severe" in 6.1% of active and none in the sham. All other adverse events were very infrequent across all groups. The eTMS protocol is conducted at 50% MT, unlike the standard rTMS 10 Hz protocol, which is conducted at 120% MT. Reduction of % MT intensity reduces site pain. Intensity is reduced when using eTMS protocols when a participant indicates discomfort at the starting intensity of 50% MT. No serious adverse event occurred during the pilot phase of a sister trial to this trial (MeRT-005).

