All subjects who finish BL assessments and meet inclusion/exclusion criteria will be randomized into one of two groups, "Active eTMS" and "Sham eTMS", in a 1:1 ratio, stratified by clinic. Stage 2 will consist of a randomized period and an open-label period. During the randomized period, the Active eTMS group will receive Active eTMS and the Sham eTMS group will receive Sham eTMS twice per day, with 20 total treatments delivered in a 2 or 3-week period. Following the randomized period of the study, all Sham eTMS subjects will have the option of participating in the open-label portion of the study. Those who choose to participate in open-label treatment will receive 20 Active eTMS sessions, twice per day, which must be completed in a period of 21 calendar days.

All groups will undergo an assessment of symptoms at baseline, before Week 6 (F1), and then again at the end of Week 10 (F2). The primary efficacy endpoint, and outcome time point, is Wave Neuroscience, Inc. Protocol eTMS-PTSD Rev 1.1 11 January 2024 PAGE 28 change in Post-Traumatic Stress Disorder symptoms between the Baseline (BL) and the first follow-up (F1). The primary efficacy outcome will be measured using the PCL-5. Safety outcomes will be measured by recording adverse events, incidence and type.

PARTICIPANT POPULATION

The enrollment goal for the combined two stages of the study is 170 participants of any gender or ethnic background, age 22-65 years, with Post-Traumatic Stress Disorder. Thirty (30) participants will be part of Stage 1 and be provided with open-label treatment to evaluate safety of eTMS in this population. 140 participants will be part of Stage 2, randomized to either active or sham eTMS, in a 1:1 allocation ratio, stratified by recruitment site. Participants randomized to sham eTMS in Stage 2 will receive an additional series of open-label active eTMS following the randomized portion of Stage 2.

Inclusion Criteria

Participants must meet all following inclusion criteria to qualify for enrollment into the study:

- 1. Willing and able to consent to participate in the study via signed Informed Consent
- 2. Age 22 65 years
- 3. Provisional diagnosis of PTSD according to Veterans Administration PCL-5 rubric fulfillment AND cutpoint score of 31 or above
- 4. Positive identification as either a Veteran, or First Responder (e.g., emergency medical service provider, firefighter, or any other emergency response personnel)

Exclusion Criteria

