In the randomized, blinded, Stage 2 of the trial, post-trial access to the active study treatment will be provided. For both ethical and recruitment purposes, there will be up to 20 additional treatments of open-label active eTMS treatment offered to participants who are part of the Sham eTMS Group who complete 75% of their assigned blinded treatment (15 treatments), unless the site PI in consultation with the Medical Monitor deem active treatment not to be in the best interests of the participant or of the study personnel (e.g., if the participant begins medications that lower seizure threshold, or experiences an adverse event such as a negative health or psychological event that would have excluded them from the blinded study).

Basis of Study Treatment Parameter Selection

Treatment with rTMS (repetitive transcranial magnetic stimulation) requires the specification of many treatment parameters. Within-session parameters that must be specified include stimulus waveform (square wave, triangle wave, sine wave), coil geometry (depth-focality tradeoff), field intensity, frequency of stimulation during the pulse train, duration of the pulse train, duration of the quiet period, number of pulse train-quiet period cycles in the treatment session. Course-of-treatment parameters that must be specified include the number of treatment sessions and the spacing of sessions.

As is the case with many forms of medical treatment, understanding of the mechanism of rTMS action is incomplete. A review by Leuchter, et al. (Leuchter, Cook, Jin, & Phillips, 2013) considered the mechanism of action in rTMS treatment of depression. The authors concluded that benefits of rTMS were tied to enhanced neuroplasticity and the resetting of corticothalamic pathways. While this assessment may provide a conceptual basis for an understanding, it does not provide quantitative specification of treatment parameters. This being the case, our best recourse was to review the prior clinical literature.

The greatest body of prior experience is in the treatment of depression. Most rTMS treatments for depression were carried out with standardized stimulation parameters, typically left dorsolateral prefrontal cortex using 10 Hz stimulation at 120% of motor threshold. The early cleared rTMS devices used this standard 10 Hz protocol – largely 37.5-minute sessions, 5 days

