SAFETY

Adverse Events

An adverse event (AE) log will be kept. There will be data collection of AEs at all follow-up visits (F1, F2, F3) as well as recording of AEs reported to the treating personnel, or other medical personnel at the treatment site, at each treatment visit and AEs that are otherwise spontaneously reported. The Side Effects Questionnaire (SEQ) will be used to ensure full reporting of adverse effects of the study treatment and procedures. When an AE is noted by the Study Coordinator/Technician it will be escalated to the Site Investigator, or their medically qualified designee as appropriate, and in all cases for an SAE. All AEs and SAEs will be reported to the Data and Safety Monitoring Board. As noted above in the section on Unblinding, the PI will keep a log of unblinded adverse event data that may be used to call a for-cause DSMB meeting to conduct a safety review. AEs will be reported to the FDA and the IRB on the schedules determined by these oversight bodies, according to instructions for reporting differing types, severity, and relatedness, of AEs.

An adverse event (AE) is defined as any untoward medical occurrence in a participant treated with an investigational product and does not necessarily have to have a causal relationship with the treatment under investigation. An AE can therefore be any unfavorable and unintended sign, symptom, or disease temporally associated with the use of an investigational product, whether or not considered related to the investigational product.

Anticipated adverse device effects for purposes of both Stage 1 and Stage 2, in order of most common to least likely to occur, include:

- Headache and neck pain
 - \circ Sponsor's clinical use history ~15%.
 - rTMS: Headache ~23%, Neck pain ~12% of rTMS cases in general. (Machii, Cohen, Ramos-Estebanez, & Pascual-Leone, 2006)
 - Generally related to muscle tension.
 - Responds well to analgesics
 - Generally, resolves within the first week of therapy.
 - Short-term only. No long-term implications.
- Application site pain/discomfort
 - Sponsor's clinical use history ~5%
 - Generally, results from pressure placed against the scalp as opposed to stimulation.
 - Generally, resolves within the first week of therapy.
 - Short term only. No long-term implications.
- Eye pain
 - \circ Sponsor's clinical use history ~5%
 - Pressure may be felt in the back of the eyes during therapy, but this does not last more than a few seconds following the pulse train.

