- There is a reasonable possibility that the treatment caused the adverse Suspected event. "Reasonable possibility" means there is evidence to suggest a causal relationship between the treatment and the adverse event. This is a lesser degree of certainty about causality than the conclusion that the adverse event was caused by the treatment. (21 CFR 312.32(a) A causal relationship requires a temporal relationship to exist between the adverse event onset and administration of study treatment. Strong evidence exists that the study treatment caused the adverse Definitely Related event. There is a temporal relationship between the event onset and administration of the study treatment. There is strong therapeutic evidence that the event was caused by the study treatment. The participant's clinical state and concomitant therapies have been ruled out as a cause.

All participants who have been exposed to study treatment will be evaluated for adverse events. All adverse events will be evaluated beginning with onset, and evaluation will continue until resolution or recovery is observed or until the Investigator determines that the participant's condition is stable, whichever is earlier. The Investigator will take all appropriate and necessary therapeutic measures required for resolution of the adverse event. Any medication necessary for the treatment of an adverse event must be recorded on the study Concomitant Medication form. If more than one distinct adverse event occurs, each event will be recorded separately.

Adverse Event Reporting

The study period during which adverse events must be reported is defined as the period from the initiation of any study procedures to the end of the follow-up data collection. The study procedures initiation is defined as beginning at the BL Visit. Every treatment visit is accompanied by adverse event data collection and adverse event data will be collected at all follow-up data collection visits. This data collection will use a side-effects questionnaire in order to methodically detect expected side effects.

Reporting of Serious Adverse Events and Unanticipated Adverse Device Effects

All Serious Adverse Events (SAE), Unanticipated Adverse Device Effects (UADE), and Serious Unanticipated Problems (UPIRTSO) that occur during the study, including death, must be reported within one working day by telephone to the IDE Sponsor, and followed up in writing

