Adverse events (AEs) will be summarized using MedDRA terms. AEs will be listed and summarized by system organ class, preferred term, incidence, severity and duration. Monthly safety summaries will be made for all study participants and listed by site and study treatment assignment and distributed to the Study Chair and Principal Investigator, who also will receive SAE reports in real-time. These listings will be produced for every DSMB meeting. The DSMB, the Study Chair and Principal Investigator will not be blinded to treatment assignment for any AE-related data.

STATISTICAL ANALYSIS PLAN FOR STAGE 2

Statistical Analysis Software

Statistical analyses will be performed using software such as the SAS® system, IBM SPSS, or EXCEL.

Analysis Populations

Two analysis populations are defined for Stage 2:

• The Intent-to-treat (ITT) analysis population includes all eligible and randomized participants

• The Per-Protocol (PP) analysis population includes all participants in the ITT population who (1) had all efficacy evaluations at the major study time points defining the primary outcome comparison, i.e., BL and F1, (2) who had no major protocol deviations, and (3) who received at least 75% of assigned blinded study treatments

Analysis of Safety

Adverse events (AEs) in Stage 2 will be summarized using MedDRA terms. AEs will be listed and summarized by system organ class, preferred term, incidence, severity and duration. Monthly safety summaries will be made for all study participants and listed by site and study treatment assignment and distributed to the Study Chair and Principal Investigator, who also will receive SAE reports in real-time. These listings will be produced for every DSMB meeting. The DSMB, the Study Chair and Principal Investigator will not be blinded to treatment assignment for any AE-related data.

Analysis of Efficacy

The tests of the primary and secondary efficacy outcomes will be hierarchical in order to constrain Type I error. If the test of the primary outcome shows a significant beneficial effect with a two-sided p-value ≤ 0.05 , the secondary efficacy outcome analysis will be conducted at a two-sided alpha = 0.05 level. If alpha has been spent in DSMB efficacy monitoring, the alpha level apportioned to the primary results analyses will be accordingly reduced.

Primary outcome efficacy analysis

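### The Stage 2 safety listings group adverse events by assigned arm with no rule for events after sham participants start open-label active eTMS, so read literally they dilute the active-versus-sham comparison

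*Combined protocol and SAP*

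**What the plan says.** The Stage 2 Analysis of Safety section has two sentences on how adverse events are presented. One gives the summary dimensions: "AEs will be listed and summarized by system organ class, preferred term, incidence, severity and duration". It names no arm, period or treatment received. The other covers the routine listings: "Monthly safety summaries will be made for all study participants and listed by site and study treatment assignment". These go to the Study Chair and Principal Investigator and are produced for each DSMB meeting.

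Under Analysis Populations, "Two analysis populations are defined for Stage 2", namely ITT and per protocol. There is no safety or as-treated population and no treatment-emergent definition.

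Crossover runs one way. The Open Label Treatment section says "there will be up to 20 additional treatments of open-label active eTMS treatment offered to participants who are part of the Sham eTMS Group", provided they completed 75% of their blinded sessions. The Participant Population section is firmer: "Participants randomized to sham eTMS in Stage 2 will receive an additional series of open-label active eTMS following the randomized portion of Stage 2". The Stage 2 design section and note 1 to Table 6 make it optional.

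The Adverse Event Reporting section sets the reporting window as "the period from the initiation of any study procedures to the end of the follow-up data collection". Events are recorded at every treatment visit, including the open-label visits in Table 6, and at F1, F2 and F3.

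**The concern.** Assignment is fixed at randomisation. Note 1 to Table 6 still calls the people entering open label sham-assigned. A listing by assignment over the whole reporting window therefore gives the active column one active course, and gives the sham column one sham course plus, for those who opt in, an active course. The sham column also gains extra treatment visits at which the Side Effects Questionnaire prompts for symptoms.

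Safety is part of the study objective and of Stage 2's stated purpose, and the DSMB sees these listings at every meeting. The Study Chair and Principal Investigator are unblinded to adverse event data, so an attribution rule chosen later would be chosen with the events in view. The same listing sentence also appears in the Stage 1 plan, where there is a single arm and no crossover to deal with.

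**Working it through.** The documents state no figure for a between-arm safety comparison, so there is none to reproduce.

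**1. Can the period be recovered from the visit?** Not reliably.
- F1 falls at RD+10 to RD+21. Open label starts within 60 days of F1, so as late as about RD+81 (21 + 60), and may run 21 days.
- F2 is at RD+71 to RD+77, so it can fall before, during or after a sham participant's active course.
- F3 (RD+176 to RD+196) comes after it.

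The split needs the onset date and the first open-label session date.

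**2. General form.** Let a be the event rate over an active course and u the share of the sham arm that opts in. For an event that does not occur under sham:
- sham column = u × a
- displayed difference = a − ua = a(1 − u)

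**3. Illustration with the rates in the rTMS section.** The protocol cites a review: "Site pain was reported by 35.8% in active TMS group and 3.8% in the sham group". Write pa = 0.358 and ps = 0.038. Two assumptions about who is affected in the second course bracket the result:
- Independent periods: sham column = ps + (1 − ps) × u × pa
- Same people affected again: sham column = ps + u(pa − ps), so the difference is 32.0 × (1 − u) points

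| Opt-in u (assumed) | Event only under active | Site pain, independent: sham column | Difference (points) | Site pain, same people: difference (points) |
|---|---|---|---|---|
| 0% | a | 3.8% | 32.0 | 32.0 |
| 50% | 0.50a | 21.0% | 14.8 | 16.0 |
| 75% | 0.25a | 29.6% | 6.2 | 8.0 |
| 90% | 0.10a | 34.8% | 1.0 | 3.2 |
| 100% | 0 | 38.2% | −2.4 | 0 |

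For example, at 100%: 0.038 + 0.962 × 0.358 = 0.382, and 35.8 − 38.2 = −2.4. Under independence the difference reaches zero at u = 0.320 / (0.962 × 0.358) = 0.93. That break-even is specific to these two rates. The differences do not depend on arm size, so the 120 and 140 randomised given in different sections lead to the same table.

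**4. The sponsor's own rate.** The Adverse Events section gives about 5% for application site pain. Full opt-in would then add about 0.962 × 5 = 4.8 points to the sham column, against 0.962 × 35.8 = 34.4 with the review's rate.

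**5. Share of active exposure affected.** With 1:1 allocation and a full course for everyone who starts one, the fraction of Stage 2 active courses listed under sham is u / (1 + u): one third at 50% opt-in and one half at 100%.

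**The case against.** The strongest reply is that this is silence, not a wrong rule, and that safeguards exist elsewhere. Much of that stands.

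- A reader might infer that the SAP defines open-label events as sham events. It does not. The by-assignment sentence governs the monthly and DSMB listings. The final summary has no stated grouping, and no active-minus-sham safety estimate or test is specified.
- A reader might infer that a seizure or manic episode in open label would be hidden. It would not. Serious events reach the sponsor within one working day and a narrative follows; the Study Chair and Principal Investigator receive these reports in real time; seizures go to the IRB and FDA within 10 days. Relatedness is graded per event and requires a temporal link to treatment. Open-label days carry their own OD label.
- The site-pain rates come from a review of other rTMS studies. The same section contrasts standard rTMS at 120% of motor threshold with 50% here, and says that lower intensity reduces site pain. The sponsor's figure is about 5%, mostly attributed to pressure on the scalp. A true 32-point excess in this trial is therefore not supported.
- Reversal at the review's rates needs about 93% opt-in, from a group that must complete 75% of sessions and remain eligible. The plan assumes 10% loss to follow-up.

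What remains is the aggregate count. Individual narratives do not correct a column total. Relatedness is named under Study Outcomes but not among the summary dimensions in Analysis of Safety. The DSMB is unblinded to assignment, which is the label that misplaces these events. The OD labels make a split possible, but no section calls for one.

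**Conclusion.** The gap is real: no rule attributes adverse events after crossover, and the only stated grouping, taken literally, lists events under active open-label eTMS as sham. The effect is dilution of about a(1 − u) for an event confined to active stimulation. This assumes equal event rates in blinded and open-label active courses and counting over the whole reporting window.

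The opt-in share is not given, so the size can only be shown as a range, from no dilution at 0% to complete loss of the difference at 100%. The site-pain table shows the mechanism and is not a forecast. The documents do not support saying that the safety signal will vanish or reverse, or that single serious events would go unnoticed.

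The primary efficacy comparison, BL to F1, is untouched. This should be fixed, but it does not threaten the trial's main result.

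**What to change.** In Analysis of Safety, and in the specification of the DSMB listings, replace the single grouping with four displays:

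1. **Blinded period:** events with onset from the first blinded session to F1, by arm. This is the main active-versus-sham safety comparison.
2. **Follow-up without open label:** events after F1 and before any open-label session, by assigned arm. This includes all post-F1 events in active-assigned participants and in sham participants who never cross over.
3. **Open label:** events from the first open-label session onward, in a separate sham-to-active column.
4. **All active exposure pooled.**

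Classify each event by the treatment received, or last received, at onset. Give the number of participants and of treatment visits as denominators in each period. State that the final adverse event summary uses the same structure.

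The cost is SAP wording and one derived variable, built from the adverse event onset date and the date of the first open-label session. Visits, sample size and treatment do not change.

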provide the diagnosis (i.e., the CAPS-5), a simple summation of severity scores across the 20 items may be used to determine probable PTSD. Initial research indicates that a cut off score of between 31 and 33 signals probable PTSD. (U.S. Department of Veterans Affairs, 2022) (Spoont, et al., 2013) A provisional PTSD diagnosis can be made by treating each item rated as 2 = "Moderately" or higher as a symptom endorsed, then following the DSM-5 diagnostic rule which requires at least: 1 B item (questions 1-5), 1 C item (questions 6-7), 2 D items (questions 8-14), 2 E items (questions 15-20). In order to avoid enrolling persons who do not have PTSD, criteria for the diagnostic rubric must be fulfilled AND a minimum PCL-5 score of 31 will be required. Evidence for the PCL for DSM-IV suggests that a 5-10 point change represents reliable change and a 10-20 point change represents clinically significant change. It is recommended to use 10 points of change as a minimum threshold for determining whether the improvement is clinically meaningful. Change score characteristics are currently being determined regarding reliable and clinically meaningful change. The VA recommends following the DSM-IV recommendations. The PCL-5 is the primary efficacy outcome for Stage 2 of this trial. Morrison et. al., in the first study on the PCL-5's psychometric properties for first responders in the United States, studied a sample of 133 first responders, including firefighters/EMT (76.7%) and police (23.3%). The mean total PCL-5 score was 38.73 (SD = 18.68, range 0-72). (Morrison, Su, Keck, & Beidel, 2021)

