
Stage 2

Stage 2 of the trial is intended to investigate efficacy and safety of the procedure in the target population. The primary efficacy outcome is a measure of PTSD symptom severity. PTSD symptom reduction will be calculated as the arithmetic reduction in PCL-5 scores between BL and F1. See the above Data Collection section for a description of this assessment.

Safety will be characterized by adverse event incidence, relatedness, severity, type, subsequent treatment/intervention required, and resolution status.

SAMPLE SIZE CONSIDERATIONS FOR STAGE 1

A convenience sample size of thirty (30) will be treated in the safety pilot stage in order to detect common adverse effects or safety concerns.

SAMPLE SIZE CONSIDERATIONS FOR STAGE 2

Sample size assumptions:

[figure not shown]
- Design variable is change in PCL-5 between BL and F1.
 - Mean in first responders = 38.73 (SD = 18.68) (Morrison, Su, Keck, & Beidel, 2021)
 - Primary outcome clinically important difference = 15(10-20) (U.S. Department of Veterans Affairs, 2022)
- Planned estimated effect size +0.8 SD_{difference}, for a difference in Active eTMS versus Sham eTMS group mean pre-post PCL-5 scores = 15, with pooled SD_{difference} = 18.68
- Assignment ratio =1:1 for Active eTMS vs. Sham eTMS
- 10% loss to followup

- Type 1 error = 0.05 (2-sided)
- Statistical power = .985
- Method of calculation Sample size and power for given detectable difference between two mean difference scores using Student's t-test according to method of Dupont & Plummer

Sample size requirements:

- Total completers: 108 (90% 54 per group) See Figure 2 below
- Total to be randomized:120 (60 per group)

FIGURE 2: Primary efficacy outcome, PCL-5. Statistical power by number of completers per treatment group for Type 1 error 0.05 (.985) and 0.01 (.938)

DATA AND SAFETY MONITORING BOARD

A Data and Safety Monitoring Board (DSMB) comprised of at least 3 **independent** subject matter, medical, clinical trial methods, and biostatistics experts will be constituted to review the protocol, recruitment progress, site performance, study conduct, and safety data. The Board will request analyses, and will make recommendations regarding study continuation, amendment, or termination, as well as the advisability of adding up to 3 additional research sites.

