Poolability over study sites will be separately assessed. In a separate analysis the association between the primary endpoint and the study site will be explored. Both the main effect of study site and the interaction between study site and treatment group will be explored.

Additional Analyses of the Primary Outcome

Exploratory responder analyses will be conducted. To determine whether a greater percentage of Active-treated participants respond to study treatment than Sham-treated participants, the binomial z-test will be used to compare the Active-treated group to the Sham-treated group at a number of percentage reductions in PCL-5 scores as candidate values of a successful treatment response. A range of percentage reduction values will be investigated as possible discriminating values to assist in designing future trials regarding sample size justification and power analysis, should a trial in future be designed with a responder analysis as the primary outcome or a secondary outcome.

Other participant reported outcomes analyses

Other participant reported outcomes, including assessment of blinding, will be analyzed according to their level of data (e.g., quantitative, rank order, or categorical) and validity of statistical assumptions required (e.g., homoscedasticity and normality).

Electrophysiological data analyses

Quantitative EEG data collected at BL and F1 will be stored on hard disk and analyzed offline. Raw data of each record will be visually inspected to reject significant artifact contamination. Selective data will be further analyzed by fast Fourier transform (FFT) routine to yield four consecutive frequency bands – delta (0.5-4 Hz), theta (4-8 Hz), alpha (8-13 Hz) and beta (13-35 Hz). Power density of each frequency band of each channel will be used to measure the EEG changes after treatment. Statistical analysis will include data reduction by initial factor analysis. Difference between treatment groups at each recording time will be tested by repeated measures and regression of number of treatments by channel. It is anticipated that successful treatment will result in reductions in low frequency rhythms and increases in peak alpha frequency and correspondent narrow-band density. These changes in EEG variables will be further correlated with clinical and cognitive data to explore the hypothesis that EEG parameters could be a biomarker for PTSD.

STUDY SITE MONITORING

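### The SAP gives a protected 0.05 test to a secondary efficacy outcome that is never named, so this step does not control error once the primary succeeds

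*Combined protocol and SAP*

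**What the plan says.** Under Analysis of Efficacy (Statistical Analysis Plan for Stage 2) the plan says: "The tests of the primary and secondary efficacy outcomes will be hierarchical in order to constrain Type I error". If the primary reaches a two-sided p-value of 0.05 or less, "the secondary efficacy outcome analysis will be conducted at a two-sided alpha = 0.05 level". The same paragraph reduces the primary's alpha if some has been spent at the interim. The Data and Safety Monitoring Board section sets the levels at 0.001 for the interim and 0.049 for the final analysis.

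No secondary outcome is defined. Study Outcomes, Stage 2, and the Outcomes row of the synopsis each give a primary (PCL-5 change from BL to F1) and a safety outcome, and nothing else. The synopsis row Statistical Methods (Stage 2) uses the word secondary for the Per Protocol analyses and calls other outcomes exploratory. The Blinding section mentions primary or secondary outcome data and then treats exploratory outcomes separately.

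Additional Analyses of the Primary Outcome declares the responder analyses exploratory. They compare the arms by z-test at an unstated number of percentage reductions in PCL-5. The aim is given as: "A range of percentage reduction values will be investigated as possible discriminating values to assist in designing future trials", with sample size and power named. The PCL-5 description under Data to be collected says: "It is recommended to use 10 points of change as a minimum threshold for determining whether the improvement is clinically meaningful".

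**The concern.** A hierarchy controls error only if each step is fixed in advance. Here the second step has an alpha level but no outcome. Table 5 shows ten scales besides the PCL-5 collected at both BL and F1: DHQ, BPI, CGI, Braincheck, VR-36, PHQ-SADS, AUDIT, DAST-10, OCS and PSQI. Nothing in the plan prevents the secondary from being identified after the results are known. A claim made that way would be described as protected against Type I error when it is not. The trial is planned at very high power for the primary, so an open gate is the scenario it is designed for.

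The responder analysis raises a smaller, related issue. A cut-off picked because it separates the arms best shows too large a difference, and the plan intends this exercise to inform sample sizes.

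**Working it through.** **The plan's own figure.** Inputs from Sample Size Considerations for Stage 2: "group mean pre-post PCL-5 scores = 15, with pooled SD_{difference} = 18.68", 54 completers per group, two-sided 0.05. Noncentrality = 15 / (18.68 × √(2/54)) = 4.172. Two-sample t-test with 106 df: power 0.985, which agrees with "Statistical power = .985". If the planned effect is real, the gate therefore opens in nearly every trial. With the normal approximation at 0.049 (critical value 1.969), the probability is 1 − Φ(1.969 − 4.172) = 0.986.

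**False favourable secondary claim.** Assume k candidates, none with a true effect, and a claim for active if any reaches two-sided 0.05 in its favour. For one named outcome the chance is 0.05/2 = 2.5%.

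- Independent outcomes: 0.986 × (1 − 0.975^k). For k = 3: 0.986 × 0.0731 = 7.2%. For k = 5: 0.986 × 0.1189 = 11.7%. For k = 10: 0.986 × 0.2237 = 22.1%.
- Equal correlation ρ among all outcomes, primary included: integrate [1 − Φ((1.960 − √ρ·u)/√(1−ρ))^k] × [1 − Φ((1.969 − θ − √ρ·u)/√(1−ρ))] × φ(u) over u, with θ = 4.172 for the planned effect and θ = 0 for a null primary.

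| Primary effect | k | ρ = 0 | ρ = 0.5 | ρ = 0.7 |
|---|---|---|---|---|
| 15 points | 1 | 2.47% | 2.50% | 2.50% |
| 15 points | 3 | 7.21% | 6.27% | 5.46% |
| 15 points | 5 | 11.73% | 9.15% | 7.42% |
| 15 points | 10 | 22.06% | 14.37% | 10.65% |
| none | 10 | 0.55% | 1.64% | 1.97% |

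The documents give neither k nor ρ, so the table is a range. Counting claims in either direction, the figures for a real primary effect are about 14%, 22% and 39% for k = 3, 5 and 10 at ρ = 0, and 10%, 14% and 20% at ρ = 0.7.

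**Gate level.** The gate is written at 0.05 and the final criterion at 0.049. Read literally, a primary p-value between the two misses significance yet opens the secondary test. The numerical effect is tiny.

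**Responder search (minor).** Assumed: 11 cut-offs from 10% to 60%, 54 per arm, normally distributed percentage reduction with SD 30%, and the cut-off with the largest observed difference selected. Sham and active means of 30% and 46% are the predecessor trial's PCL-M figures (Preliminary Data). The true difference at cut-off c is Φ((46 − c)/30) − Φ((30 − c)/30). By simulation:

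- Means 30% and 46% (0.53 SD): 26.6 points observed at the selected cut-off against 19.3 true there, an excess of 7.3.
- Means 30% and 54% (0.8 SD, the plan's effect size): 35.8 against 29.3, an excess of 6.5.
- No effect: the best difference averages 7.9 points, and 11% of searches find a significant cut-off in favour of active.

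A second model assumes baseline PCL-5 of 50 (SD 11), sham change of 12, SD of change 18.68 and 4 to 13 cut-offs. With a true difference of 7.5 points it gives 20 to 21.5 points at the best cut-off against 15.7 at a fixed 30%. With a true difference of 15 it gives 34 to 35 against 30. The direction is the same and the excess is 4 to 6 points.

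**The case against.** The strongest reply is that the gate does real work. If eTMS has no effect on the primary, the secondary is rarely tested, and a false favourable claim stays at 2% or less even with ten candidates. That stands. A reader might infer that the hierarchy is worthless or that the trial's Type I error is uncontrolled. The documents do not support this: the primary test and its 0.001/0.049 levels are untouched, and the gap opens only when the primary effect is real.

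Ten candidates is also toward the high end. The SAP speaks of the secondary outcome in the singular, and drug-history, alcohol, drug-abuse and opiate-craving scales are weak choices for a PTSD efficacy claim. This stands in part, which is why 3 and 5 are shown. On the other side, the VR-36 alone yields eight domain scores and two summary scores.

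The word secondary may be leftover wording, or may mean the Per Protocol analysis. The latter is a second analysis of the same outcome, whereas Analysis of Efficacy and Blinding both refer to secondary outcomes. If it is leftover wording, deletion settles the matter. Nor do the documents say that anyone intends to choose after seeing the data; they only leave that open.

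On responders, a reader might infer that the search yields an efficacy claim for this trial, or that a later trial is bound to be underpowered. Neither follows. The analysis is labelled exploratory, lies outside the hierarchy, and is not said to end in one selected cut-off whose observed difference becomes the planning effect. Even a fixed 30% cut-off, planned for 90% power from its own observed difference, averages only about 82 to 85%, so part of any shortfall is ordinary sampling error. The 10-point threshold is not ignored either: the 10 to 20 range supports the sample-size difference. It is simply not used to define a responder.

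**Conclusion.** The concern holds for the secondary tier. The plan claims error control for a test whose outcome, time point and model are nowhere stated. Given a real primary effect, the chance of a false favourable claim is about 5 to 7% with 3 candidates, 7 to 12% with 5 and 11 to 22% with 10, against 2.5% for one named outcome. These figures assume equally correlated null candidates (ρ from 0.7 to 0) and selection of the best. The primary analysis and its 0.985 power are not in question.

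The responder point is minor. Selection inflates the difference at the chosen cut-off by about 7 percentage points under the first set of assumptions and 4 to 6 under the second. It touches this trial's conclusions only if a selected cut-off is reported as a finding.

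**What to change.** Choose one of two changes under Analysis of Efficacy:

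- Strike the secondary tier and call every non-primary outcome exploratory, in line with the synopsis.
- Name one outcome already collected at BL and F1, with its time point and model, and add it to the Stage 2 outcome lists.

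If the tier is kept, open the gate only when the primary meets its final criterion of 0.049, not 0.05.

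Under Additional Analyses of the Primary Outcome, pre-set a responder definition. The 10-point change is available, although the plan notes that it rests on evidence for the DSM-IV version of the scale. The predecessor's 30% reduction was on the PCL-M and would need justification for the PCL-5. Report all other cut-offs descriptively, as cumulative response curves by arm, and state that future sample sizes will not be planned from the best-looking one.

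The cost is SAP wording: fewer secondary claims and a less favourable responder difference. Sample size, data collection, the primary analysis and its power do not change.
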